## Randomisation and Blinding

This study is an open label parallel randomized-controlled trial hence both the research team and participants will not be blinded. However, as the randomisation will be made based on participants location, contamination of participants was minimised.

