### Randomisation and Treatment Allocation

Eligible adults who have consented to participate are matched for age, sex and ethnicity as baseline. To minimised contamination, participants were randomised to either intervention or control group based on their location.

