### *Intervention Group*

Participants residing in the location selected to be intervene will to form at minimum 4 peer groups. This group will receive a continuous three-months, peer-led nutrition and lifestyle behaviour intervention through a series of peer gathering. Two participants from each peer group will be selected as the peer leader (PL). PL will be trained to deliver the content of PERSUADE modules and will be responsible to run a weekly peer gathering with their respective groups for the following three months.

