## Outcome Assessment

All assessments will be conducted at during designated peer gathering sessions by the research team and assisted by trained PL (Table 3).

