### Primary Outcome – Metabolic Syndrome Biomarkers

Anthropometric measurements (body mass index, waist circumference and percentage of body fat) and blood pressure are taken during each follow-up sessions based on the WHO Protocol (27). Blood clinical outcomes will be screened using rapid finger-prick testing method; glucometer (B Braun Omnitest®3, Germany) and blood lipid profile meter (Cardiocheck® PA, Germany), as it is an accurate and sensitive method to cater a community setting intervention (28). Besides, a bio-impedance body composition analyser (InBody® H2OB Analyser, Korea) will be used to estimate fat and muscle percentage of the participants.

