### Statistical Analysis

Diet and nutrition data will be analysed using Axxya Systems Nutritionist Pro™ Diet Analysis while all statistical analyses are performed with IBM® SPSS® Statistics 23.0. Descriptive methods will be used to demonstrate to describe participant characteristics and the consistency of both groups. Independent t-test or Chi Square will be used to evaluate baseline characteristics of peer intervention

participants compared to control, overall significance of improvement across clinical outcome measures. As this is a RCT involving repeated measures, the ANOVA repeated measures model is applied to observe significant differences between and within the study groups. This includes change in clinical measures of MetS component from baseline, end of trial (3rd month) and follow up (6th month). The magnitude of change in both primary and secondary outcome measures will be estimated and the given 95% confidence intervals with the p value 0.05 was taken as the level of significance.

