		To identify and set a personal health goals	An infographic on healthy life style	To be able to set realistic health goals in term of body weight, waist circumference and weekly diet and physical activity planning

Table 3: PERSUADE outcome assessment

Outcome	Instrument
Socio-demographic information	A brief sociodemographic questionnaire is use to collect basic details (i.e. age, marital status, ethnicity, educational status, occupation, personal and household income, family size and number of years of residence in current location).
Lifestyle characteristics	A brief questionnaire will inquire on participants' smoking habit, alcohol consumption and sleeping pattern. A validated health-related quality of life (HRQOL) questionnaire will be used to determine subject's fulfilment of life.
Physical Activity	International Physical Activity Questionnaire (IPAQ) will be used to determine the level of physical activity of the participants.
Anthropometry	A height scale, body tape and bio-impedance machine will be used to measure participants' height, weight, waist and hip circumferences and body composition.
Nutrition and diet	A semi-food frequency questionnaire (SFFQ) and 3 days 24H food recall will be used to record the participants' nutrients and dietary intake.
Blood biomaker	Finger prick rapid method will be used to detect participants' fasting blood sugar levels and fasting lipid profile.

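### Open-label delivery does not justify leaving all outcome measurement and analysis unmasked, with intervention-arm peer leaders helping to take readings that include tape-measured waist

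*Combined protocol and SAP*

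**What the plan says.** All references are to the combined protocol and SAP.

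- **Randomisation and Blinding** describes an "open label parallel randomized-controlled trial hence both the research team and participants will not be blinded". The only mitigation offered there is allocation by location, and its stated purpose is to limit contamination.
- **Randomisation and Treatment Allocation**: "participants were randomised to either intervention or control group based on their location".
- **Outcome Assessment**: "All assessments will be conducted at during designated peer gathering sessions by the research team and assisted by trained PL". No outcome is exempted.
- **Intervention Group** and **Peer Leader Selection**: two members of each intervention peer group become its leaders, are trained in the modules and run the weekly gatherings.
- **Primary Outcome**: "Anthropometric measurements (body mass index, waist circumference and percentage of body fat) and blood pressure are taken during each follow-up sessions", following a cited WHO protocol. For glucose and lipids, "Blood clinical outcomes will be screened using rapid finger-prick testing method", with a named glucometer and lipid meter. No blood pressure device is named.
- **Table 3**, on anthropometry: "A height scale, body tape and bio-impedance machine will be used to measure" the participants, so waist is read by tape.
- **Statistical Analysis** names t-test, chi-square and repeated-measures ANOVA. It mentions no coding of arms and no locking of the analysis before arms are revealed.

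**The concern.** The plan treats unblinded delivery as if it settled the question of unblinded measurement and analysis. These are separate matters. Participants in a peer programme must know that they attend it. That does not require the people who deliver the programme to help measure its results, or the analysis to be written with arms identified.

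The documented route for observer bias is the peer leaders' role. They belong to the intervention arm, lead its sessions and assist with assessments. Waist is the most exposed of the primary measures because it is read by hand. It is also prominent in the programme: Community-relevant Approach singles it out as a risk marker, and Table 2 has participants measure it and set goals for it.

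If readings in one arm lean in the hoped-for direction, the lean has the same sign as the hypothesised effect. None of the named analyses can separate the two.

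**Working it through.** **1. Does the plan contain a safeguard elsewhere?** Read together, Randomisation and Blinding leaves the team unblinded, Outcome Assessment gives that team and the peer leaders all the measuring, and Intervention Group places the peer leaders in one arm. The outcome sections and Statistical Analysis add no masked assessor, no hiding of earlier values, no masked data entry and no coded analysis. Location-based allocation addresses contamination and in fact discloses the arm to anyone at the site. The plan does not say where control participants are measured, or whether peer leaders assist there.

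**2. Evaluable participants per arm.** Sample Size and Power Calculation gives 48 per group after 20% dropout.

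- 48 × 0.80 = 38.4, so about 38 per arm. In reverse, 38 / 0.80 = 47.5, rounded up to 48.
- Inflating by multiplication also fits: 40 × 1.20 = 48.
- The plan gives no SD for fasting glucose, so 48 cannot be reproduced from its inputs. At two-sided 0.05 and 80% power, 38 per arm implies SD = 1.5 × √(38/2) / (1.960 + 0.842) = 2.33 mmol/L for a difference of 1.5, and 2.80 for 1.8.

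The present point changes none of these inputs. I use 38 per arm below.

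**3. Illustration of what a lean would do.**

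- From the plan: 38 per arm (step 2) and significance level 0.05. Sidedness is not stated, so two-sided is assumed.
- Assumed: SD of waist change 4, 6 or 8 cm; lean b of 1 or 2 cm in one arm; no true effect; independent participants; normal approximation.
- SE = SD × √(2/38).
- P(reject) = Φ(b/SE − 1.96) + Φ(−b/SE − 1.96).

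Worked case, SD 8 cm and b = 1 cm: SE = 8 × 0.2294 = 1.835 and b/SE = 0.545. So P = Φ(−1.415) + Φ(−2.505) = 0.0785 + 0.0061 = 0.085.

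| Assumed SD of change | SE | 1 cm lean | 2 cm lean |
|---|---|---|---|
| 8 cm | 1.835 | 8.5% | 19.3% |
| 6 cm | 1.377 | 11.2% | 30.6% |
| 4 cm | 0.918 | 19.3% | 58.7% |

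With b = 0 the rate is 5%. In SD units, a lean of 0.1, 0.2, 0.3 or 0.5 SD gives 7.2%, 14.1%, 25.8% or 58.7%.

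**4. Which remedies touch the lean?** If each reading carries a constant shift b, the mean of two readings by the same measurer also carries b. Random error falls slightly, so b/SE does not shrink. Duplicate waist readings are therefore not a remedy for this problem. Coded arms protect analytic choices but cannot alter a reading already taken. Removing peer leaders from the readings, and hiding earlier values, act on the reading itself.

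**The case against.** **The size is hypothetical.** No document gives an SD for waist change or evidence of a lean. The calculation also treats participants as independent, although allocation is by location across four neighbourhoods, so 5% is not this trial's true starting error rate. The outcome used for sample size is meter-read glucose, not waist. All of this stands, and it is why the table is an illustration and not an estimate.

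**Full masking is hardly possible.** Site and setting reveal the arm. This stands. A reader might infer that masking would cost nothing. The documents give no cost, and hiding the arm from measurers would need outside assessors and a neutral or mixed venue. The remedy below does not attempt that.

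**Hand copying and sight of earlier values are not documented.** A reader might infer that staff transcribe device values and see previous readings. The plan describes no recording step and does not say what measurers can see. It supports only that they know the arm. Meter and bio-impedance outputs also leave less room for influence than a tape.

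**Analysts picking a favourable test.** A reader might infer this from the list of methods. The sentence beginning "Independent t-test or Chi Square will be used to evaluate baseline characteristics of peer intervention" mainly concerns baseline, t-test versus chi-square follows the variable type, and ANOVA is assigned to the group differences. The same sentence ends with an ambiguous reference to improvement in clinical outcomes, so some latitude remains, but the evidence for selective choice is weak.

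**Existing safeguards.** The cited WHO protocol may already standardise readings, but its content is not in the documents. Control participants also set anthropometric goals, so a waist goal is not specific to one arm. Neither point answers the peer leaders' part in measurement.

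**Conclusion.** The concern holds in a limited form. The step from open-label delivery to wholly unmasked measurement and analysis does not follow, and the plan has no safeguard against observer bias. The best-documented weakness is that intervention-arm peer leaders who deliver the programme help with assessments, including a tape-read primary measure.

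Under the assumptions stated above, a 1 cm lean takes the false-positive rate for waist from 5% to between 8.5% and 19.3%, and a 2 cm lean takes it to between 19.3% and 58.7%. These figures show sensitivity. They do not show that bias will occur, and a reader should not take them as a forecast. The sample size is unaffected. The change is worth making because the main steps need no extra assessor and protect a primary measure.

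**What to change.** Amend Randomisation and Blinding, Outcome Assessment, Primary Outcome and Statistical Analysis to state that:

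1. Peer leaders may help with logistics but neither take nor record any outcome reading.
2. Measurers cannot see a participant's earlier values when taking a new one.
3. Device readings are captured directly from the device where it allows this.
4. The analysis code is written and locked on data with coded arm labels. Location, attendance and poster counts are withheld until the lock, because each would reveal the arm.
5. Measurers will still know the arm because allocation is by location, and this is reported as a limitation.

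The cost is protocol wording, slightly more work per visit and some extra data handling. The change reduces the bias and does not remove it.

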## Development of Peer Modules

A stepwise formative research was conducted to initiate the development of an evidence-based, community-specific and culturally-sensitive peer support program. This formative step aimed to assess the need of a sustainable lifestyle intervention, to form a behavioural change objective matrix, to develop a community-relevant interventional content and finally to elucidate the most sustainable delivery method for the targeted peer population.

### Evidence-based Module

The formative research initiated by reviewing the objectives and lifestyle recommendations set in the National Strategic Plan for Non-Communicable Diseases 2010-2014 (16), Malaysian Clinical Practice Guidelines (CPG) for Primary and Secondary Prevention of Cardiovascular Disease 2017 (17) and Malaysian Dietary Guideline 2010 (15) which are the three key guidelines informing the peer modules. Furthermore, to address component specific recommendations, the peer modules were added with inputs from several other clinical practice and MNT guidelines namely, Malaysian CPG for Type 2 Diabetes Mellitus 2015 (18), Malaysian CPG for Management of Dyslipidemia 2017 (19), Malaysian CPG for Management of Obesity 2004 (20), Malaysian CPG Management of Hypertension 2013 (21), Malaysian Medical Nutrition Therapy (MNT) for Type 2 Diabetes 2005 (22), Malaysian MNT for Hyperlipidemia 2005 (23), and Malaysian MNT Hypertension 2005 (24). This is to ensure that the module is thoroughly developed in line with the published national guidelines. Additionally, published studies on MetS in Malaysia were systematically reviewed. In this review, the nutrition and lifestyle behaviour risk factors will be explored to which those may explains the notably increase of MetS prevalence in Malaysians. The review is regarded as crucial as the risk factors affecting different population were found to be distinctive (25). Eventually, four behavioural change objective themes were determined and elaborated according to the conceptual model to form a matrix containing respective change objectives as well as self-efficacy skills needed to achieve it (Table 2).

### Community-relevant Approach

PERSUADE behavioural change matrix is used as the backbone of its content development. Each modules is carefully developed using respective HBM constructs. For instance, in first module; *Metabolic Syndrome*, contents were developed to deliver the information on risk and susceptibility of MetS. Furthermore, the module is integrated with the information on the self-efficacy skills of measuring waist circumference as the most important risk of MetS. To make PERSUADE to be a community-relevant intervention, internal and surface makeover of contents were done on each module. These makeover is done using the input obtained from the focus group discussion done among Malaysian adults with MetS. During the internal makeover, contents is revised to reflects the

social, psychological, environmental and cultural influences on individuals' health behaviours. Especially that in Malaysia it spread differently across racial populations (26), a holistic understanding how the target audience perceives the disease, its risk and its susceptibility is crucial as these perceptions may influence specific health behaviours. Following that, during the surface makeover step, the content is ensured to match characteristics of the community; low-to-middle income population. As a whole, the PERSUADE module contents health were created by acknowledging the social and behavioural context of the target population.

### Intervention Poster Design

Since PERSUADE is designed for low to middle class community with limitation in technology reach, literacy and affordability, each peer modules objectives will be addressed out using an infographic poster as a stimulus for a peer discussion. Poster design and health information to be highlighted in the posters are discussed in a research panel comprising of a nutritionist, a public health expert, and a layman. The information is aimed to improve peer knowledge, giving them the ability to acknowledge their own barriers and motivations of adopting healthy nutrition and lifestyle behaviours. To increase peer engagement and enhance understandability, poster will include appropriate visual aids such photographs and illustrations. Relevant self-efficacy skills were also included to making the poster as an interactive stimulus for peer gathering sessions. Other than that, to initiate peer discussion, a list of Frequently Asked Question (FAQ) sheet will be provided together with the posters. This FAQ contains factsheets of frequent queries on MetS as gathered earlier from focus group discussions. Following that, all materials will be prepared in two languages, Bahasa Melayu and English to make it more inclusive.

### Peer Leader Selection

As an elaboration to the study flowchart (Figure 2), the intervention group will form a minimum number of eight peer groups with two PL will be selected from each group on voluntarily basis. PL will be trained for the all four modules and an extra module; health promotion. This module aimed at assessing appointed PL for leadership, health educator role, and understanding of the PERSUADE modules. All PL attended a two-days training session on focussing on leadership and communication skills. On top of that, a practical approach will be used, including physical, nutritional, and psychological aspects of a lifestyle change as included in all four PERSUADE modules. PL will be trained to engage with their peers in conversations about the issues of concern, seeking to promote health-enhancing knowledge and skills. The goal for each peer group is to be able to identify potential barriers and determinants of lifestyle improvement and subsequently take actions to reduce their CVD risk. At the end of PL training, a simple post-questionnaire will be distributed among them to indicate validity and adequateness of their knowledge and skills on all peer modules.

Respective PL will distribute the posters among their peer group every week to initiate discussion of relevant topics based on the weekly objectives. In order to maximise the participation, regular reminder about the next peer gathering sessions and short health message through text were regularly sent by PL. Peers will then have to keep the poster and returned it to the PL at the end of three months as a measure of compliance to the peer support program. Besides, peers are also encouraged to distribute the poster as a health promotion steps among the community.

## Outcome Assessment

All assessments will be conducted at during designated peer gathering sessions by the research team and assisted by trained PL (Table 3).

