### *Control Group*

Participants in the control group will receive a one-time personalised nutrition and lifestyle advised based from the Malaysian Dietary Guideline 2010 (15). They will be assured to be followed up twice for the next six month. During this session, participants will be required to set realistic health goals particularly on their anthropometric measures, blood biomarkers, dietary practice and physical activity levels.

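### All assessments are placed at peer gatherings with peer leaders assisting, which fits a described gathering only for the intervention arm at month 3; venue, assessor and leader role for controls are not stated

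*Combined protocol and SAP*

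**What the plan says.** The Outcome Assessment section gives one rule for the whole trial: "All assessments will be conducted at during designated peer gathering sessions by the research team and assisted by trained PL". It points to Table 3, which lists every outcome and its instrument, and makes no exception by arm or visit.

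Gatherings and leaders are defined elsewhere. The Intervention Group section says that the arm receiving the programme forms peer groups, that two members of each group become leaders, and that the leaders are "responsible to run a weekly peer gathering with their respective groups for the following three months". On their training, Peer Leader Selection says "PL will be trained for the all four modules and an extra module; health promotion". The module content includes "the self-efficacy skills of measuring waist circumference" (Community-relevant Approach), and Table 2 adds BMI.

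Controls receive a single advice session (Control Group). Of their later contact the plan says: "They will be assured to be followed up twice for the next six month".

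The Summary and the Statistical Analysis section set three time points: baseline, month 3 (called the end of trial) and month 6. Recruitment Process has eligible people complete the baseline questionnaire once they have consented. Randomisation and Blinding states that neither the research team nor participants are blinded.

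**The concern.** A between-arm comparison needs outcomes to be measured in the same way in both arms. Here the only stated rule on where and by whom outcomes are assessed relies on events and helpers that the text gives to one arm. Followed literally, it cannot be carried out for controls. In the intervention arm, it brings people who deliver the programme into the assessment of their own group at the visit that ends the intervention period.

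Blinding offers no protection, because the trial is open label. Waist and blood pressure depend partly on the operator. Activity, sleep, smoking, alcohol, diet and quality of life are self-reported, and answers may shift when a fellow participant who leads the programme is helping. The training described covers modules, leadership and communication. Waist and BMI appear as self-efficacy skills, and no training as an outcome assessor is described.

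**Working it through.** No figure in the plan bears on this point, and the sample size does not enter. The check sets the sections side by side and counts.

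**Step 1. Where can the rule be followed?** There are 2 arms × 3 visits = 6 combinations. For each, the question is whether the text describes a peer gathering with trained leaders.

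| Arm | Visit | Described gathering with trained leaders? | Source |
|---|---|---|---|
| Intervention | Baseline | No. The questionnaire is completed at recruitment; groups and trained leaders come afterwards | Recruitment Process; Intervention Group; Peer Leader Selection |
| Intervention | Month 3 | Yes. Weekly gatherings run for three months | Intervention Group |
| Intervention | Month 6 | No. This is three months after the programme ends | Summary; Intervention Group |
| Control | Baseline | No | Control Group; Recruitment Process |
| Control | Month 3 | No | Control Group |
| Control | Month 6 | No | Control Group |

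The rule matches 1 of 6 combinations. This takes the month-3 visit as falling at the close of the weekly gatherings. For baseline, only the questionnaire is explicitly placed at recruitment. For the baseline physical measurements, the point is that no gathering is described before the groups form.

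**Step 2. What is missing for controls?** Timing is given (Summary, Control Group, Statistical Analysis), and two follow-ups in six months agree with months 3 and 6. Instruments are given without distinction by arm (Primary Outcome, Secondary Outcome, Table 3). Venue, assessor and any leader role are not given.

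**Step 3. Which outcomes are exposed at intervention month 3?**
- More exposed: waist, blood pressure, and self-reported activity, sleep, smoking, alcohol, diet and quality of life.
- Less exposed: glucose and lipids read from a meter, and body composition read from an analyser (Primary Outcome). Fasting glucose, the variable used for the sample size, is in this group.

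**Step 4. Dietary recalls.** The Secondary Outcome section uses three non-consecutive days within a week, and a weekly gathering gives one gathering day in seven. If each recall is taken on its own day, at most 1 of 3 can coincide with a gathering and at least 3 − 1 = 2 of 3 cannot. If several days are recalled at one session, there is no conflict. The count therefore depends on the reading. It concerns logistics and says nothing about bias.

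**The case against.** The rule has the research team conducting the assessments; leaders only assist, and the extent of their help is not defined. It may be limited to calling people in and arranging the room, in which case little measurement is touched. The gatherings are described as designated, so special sessions may have been intended for controls and for month 6. Figure 2, which the plan says details the study, is not shown and may set out the visits. Lack of blinding is openly declared. This is also a feasibility trial of a peer-led programme, where involving leaders is natural.

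Much of this stands as a limit on the size of the problem. It does not remove it. The written rule still covers every assessment, still names leaders as helpers, and gives no counterpart for controls.

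Three stronger readings are tempting and are not supported:
- **That the Primary Outcome section contradicts the rule.** It says that anthropometry and "blood pressure are taken during each follow-up sessions based on the WHO Protocol". This is a different label with no venue, helper or arm, and it could mean the same sessions.
- **That the Control Group section contradicts the rule.** It is silent on where and by whom controls are assessed. The mismatch comes from where gatherings and leaders exist.
- **That the control assessment procedure is wholly absent.** Timing and instruments are stated.

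**Conclusion.** The point holds as an unworkable rule that invites measurement to differ by arm. On the text available, it fits 1 of 6 arm-by-visit combinations, and in that one it has programme deliverers helping to assess their own peers with nothing comparable described for controls. It should be corrected, with medium confidence. The conclusion assumes that gatherings and leaders exist only where the text describes them and that Figure 2 does not say otherwise.

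A reader might infer that month-3 results will be biased towards the intervention. The documents do not support that. The control setting is not stated, so a difference in conditions is itself an inference, and the direction and size of any bias cannot be determined.

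**What to change.** Replace the sentence in Outcome Assessment with one procedure for both arms, for example: *At baseline, month 3 and month 6, assessments in both arms are done by the research team with the same equipment, fasting instructions and questionnaire administration, at a comparable community venue. Peer leaders may help with invitations and logistics only; they do not measure or interview other participants.*

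Sessions need not be fully separated from gatherings and may share their day and site. Reconcile the new text with Recruitment Process, Intervention Group and Peer Leader Selection. In the Secondary Outcome section, state whether the three recalls are collected on separate days, and use the same mode in both arms.

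This is a change of wording, since the research team already conducts the assessments. The cost is somewhat longer sessions without leaders' help. It does not address the unblinded research team (Randomisation and Blinding) or allocation by location (Randomisation and Treatment Allocation). Both should be stated as remaining limitations.
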